2.7.4.4.1 Sample anti-drug antibody (ADA) status

Each ADA sample is assessed in a two tiered ADA testing approach. All ADA samples are analyzed in the initial screening assay (first tier). Samples testing positive in the screening assay are then subjected to a confirmatory assay to demonstrate that ADA are specific for AMG334 (second tier). Samples identified as positive in the confirmatory assay are considered ADA positive and are further characterized in the neutralization assay to indicate the presence of neutralizing antibodies (NAb).

The following properties of each sample will be provided in the source data:

- Positivity in confirmatory assay according to pre-specified confirmatory cut point: ADA positive (yes) or ADA negative (no)
- Presence of NAb: yes or no

Sample ADA status will only be listed. It is determined based on the following definitions:

- ADA-negative sample: Determinant sample where ADA screening or confirmatory assay is negative.
- ADA-positive sample: Determinant sample where ADA confirmatory assay is positive.
- ADA-positive NAb sample: Determinant sample where NAb ADA assay is positive.

The following definitions apply only to post-baseline ADA-positive samples with a corresponding determinant baseline sample:

- treatment-induced ADA-positive sample: ADA-positive sample post-baseline with ADA-negative sample at baseline.
- treatment-boosted ADA-positive sample: ADA-positive sample post-baseline with signal greater than the ADA-positive baseline signal.

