For safety analyses which are summarized by study phase (AE, antibody, laboratory, vital signs, ECG and C-SSRS), or during the entire study (anti-AMG334 antibody), analysis windows will be set up based on study phase:

Table 2-2Study Phases for Safety analysis

| | • | • • | | |
|-------------|---|-----------------|-----------------------|--|
| Study Phase | S | tart Time Point | End Time Point | |
| | | | | |

| Double-blind Treatment Period | For AE, concomitant medications: Study Day 1 Otherwise: Study Day 2 | For AE, concomitant medications: MIN (EoS date, last IP dose date + 27 days) Otherwise: MIN(EoS Date, MAX(last IP dose date + 27 days, EoT date+14 days)) |
|----------------------------------|---|--|
| Safety follow-up | For AE, concomitant medications: last IP dose date + 28 days Otherwise: MAX(last IP dose date + 28 days, EoT date+15 days) | For AE, concomitant medications: MIN(EoS Date, last IP dose date + 16 weeks) Otherwise: MIN(EoS Date, last IP dose date + 16 weeks +14 days) |
| Entire Study | For AE, concomitant medications: Study Day 1 Otherwise: Study Day 2 | For AE, concomitant medications: MIN(EoS Date, last IP dose date + 16 weeks) Otherwise: MIN(EoS Date, last IP dose date + 16 weeks +14 days) |

Note: all anti-AMG 334 antibody data during all periods will be included in immunogenicity analysis.

Monthly Interval for Efficacy Endpoints (from eDiary)

Monthly efficacy measurements will be calculated based on the subject's monthly investigational product (IP) dosing schedule defined below using eDiary data collected from beginning of the baseline phase (week -4 visit) up to EOT visit (week 12 visit).

| Study Phase | Assessment Time point | Interval Based on Dose | Dates |
|-------------------------------------|--------------------------|---|--|
| | | Start date | End date |
| Baseline Period | Baseline | From eDiary device assignment date (or Week -4 visit) | Day prior to study day 1 |
| Double-Blind Treatment Period | Week 4 | Study Day 1 | Week 4 dose date-1 Study day 28 if Week 4 dose is not received (either missed or IP discontinued prior to Week 4) |

Table 2-3Study Intervals for Efficacy Endpoints

| | | Note: if day 1 dose is the last IP dose subject received, the rest of monthly rates during DBTP will be calculated based on consecutive 28-day interval beginning on study day 29 (ie, 29-56 for week 8, 57- 84 for week 12) |
|---------|--|--|

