2.7.4.4 Anti – AMG 334 Antibody Formation - Immunogenicity (IG) analysis set

The number and percentage of subjects who are positive for anti-AMG 334 antibodies at baseline (Day 1, pre-dose) and who develop anti-AMG 334 antibodies (binding and, if positive, neutralizing) at any time during the study (after signing informed consent and up to the end of the DBTP) will be tabulated by treatment group.

In addition, the number and percentage of patients who develop anti-AMG 334 antibodies at any time post-dose during the DBTP (Visit 130, 150 and 1999) will be tabulated by treatment group.

The list of subjects with positive at any time will be provided.

The Immunogenicity prevalence set includes all patients in the Full analysis set with a determinant baseline IG sample or at least one determinant post-baseline IG sample.

The Immunogenicity incidence set includes all subjects in the Immunogenicity prevalence set with a determinant baseline IG sample and at least one determinant post-baseline IG sample.

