2.7.4.4.2 Patient ADA status

The following overall summaries will be provided using the Immunogenicity incidence set:

- Treatment-boosted ADA-positive: number and percent of patients with at least one treatment-boosted ADA-positive sample. The denominator is the number of patients with an ADA-positive sample at baseline.
- Treatment-induced ADA-positive: number and percent of patients with at least one treatment-induced ADA-positive sample. The denominator is the number of patients with an ADA-negative sample at baseline.
- ADA-negative: number and percent of patients with no treatment-induced or treatmentboosted ADA-positive sample.

• ADA incidence (i.e. % ADA-positive): number and percent of patients with at least one treatment-induced or treatment-boosted ADA-positive sample.

The following summaries, both overall and by time point (including baseline), will be provided using the Immunogenicity prevalence set. For summaries by time point, the denominator is the number of patients at that time point with determinant samples:

- ADA prevalence: number and percent of patients with at least one ADA-positive sample.
- NAb ADA prevalence: number and percent of patients with at least one ADA-positive NAb sample.

A listing will be provided by subject with supporting information (i.e. ADA sample status at each time point (including positive samples) and patient ADA status

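### The treatment-boosted antibody rule has no minimum rise, so assay noise alone could label up to 75% of baseline-positive patients with unchanged antibodies as boosted, in any arm

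*SAP*

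**What the plan says.** SAP 2.7.4.4.1 classifies each sample. A post-baseline sample is treatment-boosted if it is an "ADA-positive sample post-baseline with signal greater than the ADA-positive baseline signal". Neither the SAP nor the protocol gives a fold rise, a titre step or a precision margin for this comparison. The only threshold set in advance is the confirmatory cut point that separates positive from negative.

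SAP 2.7.4.4.2 classifies patients. The boosted summary is the "number and percent of patients with at least one treatment-boosted ADA-positive sample", and "The denominator is the number of patients with an ADA-positive sample at baseline". ADA incidence is then the "number and percent of patients with at least one treatment-induced or treatment-boosted ADA-positive sample". A patient with neither kind of sample is reported as ADA-negative.

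The assessment schedule (protocol Table 6-1) places antibody samples at Day 1 and at Weeks 4, 12 and 24. SAP 2.7.4.4 names the post-dose visits as "Visit 130, 150 and 1999", and the note to SAP Table 2-2 states that "all anti-AMG 334 antibody data during all periods will be included in immunogenicity analysis". The analysis sets are not restricted to active treatment: "The Immunogenicity prevalence set includes all patients in the Full analysis set" who have the required determinant samples, so placebo patients are classified by the same rule.

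**The concern.** A repeat assay of an unchanged sample will read a little higher or a little lower than the first. Under this rule any reading that is higher, by however little, counts as a boost, and the patient needs only one such reading out of several. The category should pick out patients whose pre-existing antibodies rose on treatment. As written, it also takes in most patients whose antibodies did not change.

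The summary labels make this worse. For a stable baseline-positive patient, chance decides between the ADA-positive and ADA-negative categories, and the odds are up to 3 to 1 in favour of positive. If noise alone can label 75% as boosted, a drug that truly boosted every such patient could show at most 100% against 75%, so the category discriminates poorly.

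Anti-AMG 334 antibodies are a named endpoint of the secondary safety objective (protocol Table 2-1, SAP Table 1-1), so the definition should measure what its name says.

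**Working it through.** The documents give no false-boost rate, so there is no stated figure to reproduce.

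**Inputs from the documents**
- Rise needed for a boosted sample: any amount above baseline (SAP 2.7.4.4.1).
- Boosted samples needed per patient: one (SAP 2.7.4.4.2).
- Scheduled post-baseline samples: k = 3 (protocol Table 6-1, SAP 2.7.4.4, note to SAP Table 2-2). One sentence in SAP 2.7.4.4 ends its count at the close of the double-blind period, which would give k = 2. The next sentence and the table note support k = 3.

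**Not in the documents, so treated as assumptions:** baseline positivity, assay CV, and the scale of the signal.

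**Step 1. False-boost probability with no true change.** Suppose the signal is continuous, the error is exchangeable and all samples are confirmed positive. The baseline reading is then equally likely to hold any rank among the k + 1 readings. The patient escapes the label only if baseline is the highest:

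P(boosted) = 1 − 1/(k + 1) = k/(k + 1)

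- k = 1: 50.0%
- k = 2: 66.7%
- k = 3: 75.0%

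Assay CV does not enter this formula. A simulation of 1,000,000 patients with log-normal error gave 74.9% to 75.0% for k = 3 at CVs of 5%, 10%, 20% and 30%.

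**Step 2. Relaxing the conditions (k = 3 unless stated)**
- *Missing samples.* If 10% of patients have only one post-baseline sample: 0.9 × 0.75 + 0.1 × 0.50 = 72.5%.
- *Levels near the cut point.* If each sample tests positive with probability p, P = 1 − [1 − (1 − p)^4]/(4p). This gives 73.7%, 72.2%, 68.8% and 53.1% for p = 0.95, 0.90, 0.80 and 0.50, and 26.2% for p = 0.20.
- *All post-baseline samples in one run, baseline in another.* 71%, 67% and 62% when the between-run share of variance is 25%, 50% and 75%. The limit is 50%.
- *Two-fold titres, where ties occur.* About 31%, 45% and 60% for a log2 SD of 0.3, 0.5 and 1.0.

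**Step 3. Effect on ADA incidence.** Let π be the baseline-positive proportion of the immunogenicity incidence set. The false addition is at most 0.75 × π:
- π = 1%: 0.75 percentage points
- π = 2%: 1.5 points
- π = 5%: 3.75 points

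**Step 4. What a margin would do.** With σ = √ln(1 + CV²) as the SD of the log signal, require the log rise to exceed 1.96 × √2 × σ. The chance that at least one of three samples is falsely boosted falls from 75% to 6.3%. The matching fold rise is about 1.3, 1.7 and 2.3 at CVs of 10%, 20% and 30%. A flat 2-fold rule would leave essentially 0%, 1.8% and 11.3% at the same CVs.

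**The case against.** **The reach is small.** The protocol's own antibody analysis (9.5.2) counts patients who develop antibodies and does not mention boosting; the boosted category comes only from the SAP. Safety data are not tested (SAP 2.7), and no efficacy result depends on these tables. This stands, and it limits the consequence.

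**The outputs already expose the problem.** Boosted and induced patients are reported separately with their own denominators, baseline positives are tabulated by arm, and the placebo column shows the noise level. This also stands in part. But the placebo column is a rough guide: with 330 planned placebo patients and an assumed baseline positivity of 1% to 5%, it would rest on about 3 to 17 baseline positives (330 × 0.01 = 3.3; 330 × 0.05 = 16.5). Nor does it correct the incidence reported for each active arm.

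**75% is not an expected rate.** Correct. It needs three confirmed-positive samples, a continuous signal and no shared run effect. Step 2 shows how far it can fall.

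**A reader might go further than the documents allow.**
- One might infer that false boosts make up a large share of reported ADA incidence. Protocol 3.6 says that antibody development has been infrequent, but neither document says how common pre-existing reactivity is, so the share cannot be established.
- One might infer that the rule cannot be computed, because signal is missing from the list introduced by "The following properties of each sample will be provided in the source data". That list also leaves out the screening result and determinant status, which the definitions below it need. It is evidently not exhaustive, so the omission is a wording point.
- One might infer that the rule biases the comparison against active treatment. The same rule applies in every arm, and noise by itself does not favour one.

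**Conclusion.** The point holds as a defect in the definition, not merely as missing detail: applied exactly as written, the rule misclassifies patients whose antibodies did not change. The false-boost rate is up to 75% of baseline-positive patients on the scheduled samples, 67% with two samples and 50% with one. It is lower still under the conditions in Step 2. These are shares of baseline-positive patients, not of all patients.

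The addition to ADA incidence is at most 0.75 times a baseline-positive proportion that the documents do not give. The 0.75 to 3.75 points quoted for 1% to 5% positivity are conditional on that assumption. The damage is confined to descriptive immunogenicity tables. The missing margin is certain; the number of patients it would affect is not. The correction is cheap and should be made.

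**What to change.** In SAP 2.7.4.4.1, define a treatment-boosted sample as a post-baseline ADA-positive sample whose signal or titre exceeds the patient's own ADA-positive baseline value by at least a stated fold margin. State which of the two measures is used. Derive the margin from the assay's validated precision and fix it before unblinding. Two-fold is only an example: the documents give no assay CV, and Step 4 shows that 2-fold would still leave about 11% falsely boosted at a CV of 30%.

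Add signal or titre to the source-data fields listed in the same section, so that the rule can be applied from what the SAP says will be supplied. The patient-level definitions in 2.7.4.4.2 can stay as they are.

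The cost is a few lines of SAP text and, if it is not already transferred, one extra laboratory field. Protocol 6.6.7 already allows positive samples to be characterized for titre. The downside is small: very small true rises would not be called boosted.

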2.7.4.4.2 Patient ADA status

The following overall summaries will be provided using the Immunogenicity incidence set:

- Treatment-boosted ADA-positive: number and percent of patients with at least one treatment-boosted ADA-positive sample. The denominator is the number of patients with an ADA-positive sample at baseline.
- Treatment-induced ADA-positive: number and percent of patients with at least one treatment-induced ADA-positive sample. The denominator is the number of patients with an ADA-negative sample at baseline.
- ADA-negative: number and percent of patients with no treatment-induced or treatmentboosted ADA-positive sample.

• ADA incidence (i.e. % ADA-positive): number and percent of patients with at least one treatment-induced or treatment-boosted ADA-positive sample.

The following summaries, both overall and by time point (including baseline), will be provided using the Immunogenicity prevalence set. For summaries by time point, the denominator is the number of patients at that time point with determinant samples:

- ADA prevalence: number and percent of patients with at least one ADA-positive sample.
- NAb ADA prevalence: number and percent of patients with at least one ADA-positive NAb sample.

A listing will be provided by subject with supporting information (i.e. ADA sample status at each time point (including positive samples) and patient ADA status

2.10 Patient-reported outcomes

The eDiary will collect the following patient-reported outcomes:

• HIT-6, monthly

- Beck Depression Inventory, screening

Change from baseline in headache impact scores as measured by the HIT-6 in Month 3 of the DBTP is among the secondary endpoints (see Section 2.6).

Beck Depression Inventory is collected only at screening and reported in baseline disease characteristics (see Section 2.3.2).

2.13 Interim analysis

To account for potential larger than expected variability during the DBTP of the trial, a blinded interim assessment is planned after about 50% of subjects finish their DBTP or early withdraw. Only the standard deviation of the primary variable, change from baseline in monthly migraine days in month 3, based on pooled (blinded) data from all subjects who had the opportunity to complete the week 12 assessment in the trial, will be estimated. The sample size will be increased appropriately, up to an additional 200 subjects, only if the standard deviation is larger than 5.

The type I error of the primary analysis will be maintained, as the treatment assignment will remain blinded and there is no intention to stop the study early due to efficacy.

3 Sample size calculation

A treatment difference of -1.79 days for change from baseline in monthly migraine days in Month 3 between AMG 334 140mg and placebo was observed in study 20120296 (STRIVE).

A treatment difference of -1.16 days for change from baseline in monthly migraine days in Month 3 between AMG 334 70mg and placebo was observed based on pooled analysis on the combined data from studies 20120296, 20120297, and 20120178.

Assuming a treatment effect similar to the effect observed in previous studies with AMG 334 in episodic migraine, the treatment difference in terms of change from baseline on monthly migraine days during week 9-12 (primary variable) for erenumab 140mg vs. placebo and 70mg vs. placebo is assumed at -1.5 days and -1.1 days, respectively. The common standard deviation of the primary variable is assumed at 4. Given a 2:3:3 randomization ratio among erenumab 140mg, 70mg, and placebo, a total of 880 subjects (including 10% drop out rate) would enable

| Novartis | For business use only | Page 48 |
|-----------------|-----------------------|--------------|
| SAP Amendment 1 | | CAMG334A2302 |

both doses to achieve higher than 90% power under overall 0.05 full alpha level to detect the designed treatment difference. In addition, the sample size will also ensure the trial to have adequate power to detect treatment difference under initial 2-sided 0.025 alpha level assigned to each dose (equally split between the erenumab two doses).

4 Change to protocol specified analyses

The following analyses will be performed and are not planned in the protocol

- To explore if the treatment effect varies across subgroups of interest, subgroup analysis will be performed for the primary and secondary efficacy endpoints for the following subgroups: age, gender, BMI, prior prophylactic migraine medication treatment failure (stratification factor), number of prior prophylactic migraine treatment failure medications (>=2,<2) and region.
- Given monthly migraine days is the key endpoint for the study, additional sensitivity analysis using logistic regression model will be performed for the 50% responder analysis as well.
- To evaluate the effect of AMG 334 compared to placebo on the change from baseline in HIT-6 total score during the entire DBTP (and not only at Month 3): change from baseline will be analyzed using Method II (see Table 2-4) and categorized HIT-6 score will be summarized by shift tables from baseline to the last month of the double-blind period.
- To assess the impact of long-lasting migraine events on the primary analysis, supplementary analysis has been added for the change from baseline in MMD.
- To assess the impact of patients with baseline MMD>=15 on the primary analysis results for the primary and secondary endpoints, supplementary analysis on patients with baseline MMD<15 has been added.
- Due to the eDiary device set-up, it is not possible to link a medication to an aura without headache (as no id available that link between medication taken and aura or headache event and no start/end date was collected for aura without headache event). Therefore, it is not possible to know if patient took a migraine-specific medication to treat an aura without headache and to count those days as migraine days (and thus headache days).
- During the blinded review of the baseline data, it was spotted that approx 60% of the patients didn't use any migraine-specific medication during the baseline period. Therefore, the secondary objective "To evaluate the effect of AMG 334 compared to placebo on the change from baseline in monthly acute migraine-specific medication treatment days" was exchanged

and the testing strategy (Figure 9-1 in protocol)

was replaced by a testing strategy where the endpoint MMSMD (monthly migraine-specific medication days) is tested after 50% responder and HIT-6.

5 Appendix

5.1 Imputation rules

Subjects may miss specific data points for a variety of causes. In general, data could be missing due to a subject's early withdrawal from study, a missed visit, or inability to evaluate an endpoint at a particular point in time. For this study, most of the efficacy endpoint will be collected via eDiary and subjects could miss entering several days of data in each 28-consecutive day interval. The general procedures outlined below describe what will be done when a data point is missing.

5.1.1 Study drug

Date of first study drug administration (Day 1)

Day 1 is defined as the first day of administration of randomized study drug (AMG334 or matching placebo). All other days will be labeled relative to Day 1. If subject will not be dosed at Day 1, the Study Day 1 is defined as day of randomization.

Date of last study drug administration

The date of last dose of randomized study drug is simply the day of the last dose.

5.1.2 AE and Concomitant medication date imputation

Missing or incomplete dates will be listed as it is in any listings. Incomplete start date of an adverse event or concomitant medication taken will be handled by following rule:

| | Missing | Imputation | Exception |
|---|----------------|---------------|---|
| Start date (AE, concomitant medication) | Day | 01 | Default to Study Day 1 if an adverse event starts the same year and month as Study Day 1 |
| | Day/Month | 01Jan | Default to Study Day 1 if an event started the same year as Study Day 1 |
| | Day/Month/Year | No imputation | |

For concomitant medication, incomplete end date will be imputed as follow:

| Missing | Imputed date |
|-----------|---|
| Day | The earliest of (last day of the month, date of death). |
| Day/Month | The earliest of the (31DECYYYY, date of death). |

| Novartis | For business use only | Page 50 |
|-----------------|-----------------------|--------------|
| SAP Amendment 1 | | CAMG334A2302 |

| Day/Month/Year | No imputation |
|----------------|---------------|
|----------------|---------------|

If the imputed end date is less than the existing start date, use the start date as the imputed end date.

5.1.3 **Prior therapies date imputation**

For prior medications with a stop date prior to the treatment phase (not possible to be at or after first drug administration), the start date will be imputed as the earliest possible start date and the stop date as the latest possible stop date:

For a missing/incomplete start date the minimum of the following will be imputed:

- The maximum of the earliest possible start date and the imputed birth date;
- The latest possible start date;
- The latest possible stop date.

For imputed birth date please use: date of informed consent-age-1.

For a missing/incomplete stop date the maximum of the following will be imputed:

- The minimum of the latest possible stop date and the date of first drug administration 1;
- The earliest possible stop date;
- The earliest possible start date.

Here, the earliest (latest) possible date is defined as:

- The date itself if it is complete;
- The date of the first (last) day of the month, if month and year are available but day is missing;
- The date of the first (last) day of the year, if year is available but day and month are missing;
- A very early (late) date, e.g., 01JAN1000 00:00hrs (01JAN3000 23:59hrs), if the date is completely missing.

